### **Baseline Assessment**

The study assessor will meet with each eligible patient as close to the time of discharge as possible. The study assessor will conduct the visit by phone or VA Video-Connect (VVC). The study assessor will obtain informed consent from the patient and then administer the baseline assessments, which are described under the outcome measures (see below). The baseline visit will take approximately 90 minutes to complete.

## Research Protocol/Protocol Addendum Template

---

**BESST Intervention Description:** Patients assigned to the BESST intervention will receive the BESST Intervention plus the standard care. The BESST intervention is an adaptation of the VA BIC intervention and designed to meet the unique needs of Veterans receiving care in a VA-CCN mental health treatment setting (**see BESST Manual**). BESST can be delivered by a trained mental health staff member, such as a mental health nurse, social worker, psychologist, or psychiatrist. The intervention targets the needs of patients who are being discharged from a higher-level care setting (e.g., acute inpatient, residential). The intervention incorporates aspects of motivational interviewing (MI) techniques. Because the intervention is intended to complement and enhance standard care, patients assigned to the BESST intervention will continue to have access to care (described below). There are no restrictions on the types of treatments that patients may pursue after discharge from the VA-CCN mental health treatment setting.

**Brief Educational Intervention:** Patients receive a one-hour, one-on-one, brief educational intervention on suicide prevention. The session is performed by a intervention staff member. The intervention will be delivered virtually either by telephone or VVC. We expect that this visit will occur approximately within 1-2 weeks after study entry. Because the intervention staff member will not be able to visit with the patient in person because patients may be admitted to VA-CCN units across several states (e.g., NH, MA, ME, and CT), the staff member will send the patient any associated educational handouts as shown in the manual by U.S. mail. In addition, the handout will also be available to the patient through a Qualtrics survey link (web-based) which the intervention staff member will give to the patient at the time of the session. The Qualtrics survey platform is being used for the sole purpose of making sure that the patient can see the educational materials while the intervention staff member walks through them. The patient will not answer any questions on the survey link (i.e., the link contains no questions). The patient will not put in any personal information on the website (i.e., the link contains no mechanism to enter personal data or information). The Qualtrics survey link only contains uploaded educational materials that are generic to the prevention of suicide in a Veteran population. The survey link does not contain any PHI.

The educational session is designed to meet the information needs of Veterans receiving VA-CCN mental health care and to address patient barriers to follow-up. The education includes a discussion of the patient's safety plan. The sessions are highly interactive, allowing time for questions and providing patients with written materials that they can keep for future reference.

**Regular Contact:** The patients will maintain regular contact with the intervention staff member for a total of seven contacts over the course of the three months after discharge. At each of these contacts, the intervention staff member will monitor the patient's symptoms, assess treatment adherence, review the safety plan with the patient, and, if necessary, assist the patient with engaging in care. The contacts are designed to be highly interactive, allowing time for questions and providing patients with written materials that they can keep for future reference. Depending on the patient's preference, the regular contacts will be delivered over the phone (or VA Video Connect) or in-person in a private office on the grounds of the WRJ VAMC. These visits last roughly 15-30 minutes.

**Standard Care:** Regardless of study assignment, all patients will have access to standard care. This includes recommendations for mental health follow-up as deemed appropriate by the discharging treatment team. Patients may also be offered specific treatments to address their mental health symptoms after discharge. It is also conceivable that a patient may be on the High Risk for Suicide List. Patients on the High Risk for Suicide List receive enhanced oversight as

## Research Protocol/Protocol Addendum Template

outlined in VA policy. This includes a requirement that the treating provider schedule the patient to be seen four times within the first 30 days following discharge. The primary care or mental health provider is also expected to tailor the patient's treatment to address his/her unique risk factors for suicide. The suicide prevention coordinator places a pop-up flag in the medical record to alert providers of the patient's high-risk status. The continued need for the patient to remain on the High Risk for Suicide List is reassessed by the suicide prevention coordinator. Finally, the treating provider is expected to complete a safety plan with the patient.

**Table 2: Overview of Standardized Assessment Measures and Timing of Assessment**

	Measurement Methods					Timing of Assessment		
	Instrument	Cronbach's $\alpha$	Length	Time*	0M	1M	3M	
Outcome								
Suicidal Ideation	BSS	0.87 – 0.97	21 items	10	X	X	X	
Hopelessness	BHS	0.87 – 0.93	20 Items	10	X	X	X	
Self-Efficacy	GSE	0.76 - 0.90	10 items	3	X	X	X	
Connectedness	INQ-15	0.89 – 0.91	15 items	5	X	X	X	
Connectedness	MSPSS		12 items	5	X	X	X	
Engagement	SRCS	0.89	17 items	5	X	X	X	
Suicide Attempts	CSSR-S	N/A	7 items	5	X	X	X	
Substance Use	TLFB	N/A	6 items	2	X	X	X	
Estimated time (in minutes) to complete assessments					45	45	45	

BHS = Beck Hopelessness Scale; BSS = Beck Scale for Suicidal Ideation; CSSR-S = Columbia Suicide Severity Rating Scale; GSE = General Self-Efficacy Scale; INQ-15 = Interpersonal Needs Questionnaire-15; M = months; MSPSS: Multidimensional Scale of Perceived Social Support; N/A = Not applicable; SRCS: The Suicide-Related Coping Scale; TLFB = Timeline follow-back

\*Time is described in minutes

**Outcome Measures:** As outlined in **Table 2**, we will use several standardized instruments to collect information on primary and secondary outcomes throughout the study. Copies of the assessment tools are available in the Assessment Manual.

**Baseline Characteristics:** We will collect socio-demographic data from the electronic medical record such as age, sex, marital status and service history (e.g., branch, era, combat exposure). We will also collect diagnostic information using either the MINI International Neuropsychiatric Interview (MINI), which has been validated against the Structured Clinical Interview for Diagnostic and Statistical Manual of Mental Disorders (DSM). The MINI is a short, structured diagnostic interview that, on average, takes about 15 minutes to administer. We will ask about any history of suicide attempts using the validated Columbia Suicide Severity Rating-Scale (C-SSRS). The C-SSRS includes a seven-item subscale that assesses for actual and interrupted suicide attempts.

**Primary Outcome (Suicidal Ideation):** The primary outcome will be assessed using the Beck Scale for Suicidal Ideation (BSS) (Specific Aim 1). Patients will be asked about their current suicidal ideation (i.e., past week) at baseline and at the one-month and three-month follow-up

## Research Protocol/Protocol Addendum Template

---

assessments. The BSS is a self-reported questionnaire that assesses severity of suicidal ideation. The BSS measures attitudes, behaviors, and plans to die by suicide. Each item on the BSS is scored on a scale from 0 to 2 and the first 19 of the 21 items are used to calculate a total score ranging from 0 – 38. The BSS has high reliability and is a valid measure of suicidal ideation. The BSS may be a measure of risk of suicide. There is evidence that the BSS is measurement invariant across time.

**Secondary Outcome (Patient Engagement):** We will measure patient engagement in treatment at baseline and at follow-up assessments in two ways. First, we will examine healthcare utilization in the first three months after discharge. We will look at the amount of contact with mental health providers as well as the time to first mental health appointment after discharge. We will also evaluate evidence of disruptions of care such as no-show and cancelled appointments. We will abstract these measures from the electronic medical record. Since it is possible that some patients may receive portions of their care outside of the VA system, we will also ask patients to self-report on non-VA care. To gather data regarding the patient's sense of self-efficacy around managing their suicide risk after discharge, we will administer the validated Suicide-Related Coping Scale (SRCS). This SRCS includes 17 questions related to a patient's perception of their ability to cope with suicidal thoughts. Each item is assessed using a 5-point Likert scale and the measure has been developed based on two studies of suicide prevention strategies conducted within Veteran populations. The scale includes two subscales including an External Coping subscale and an Internal Coping Subscale. Both subscales have shown good acceptable internal consistency. The two factors are also sensitive to change over time. Higher scores on the scale suggest better coping. In addition to the SRCS, we will also measure the patient's general sense of self-efficacy using the General Self-Efficacy Scale (GSE). This is a valid scale of self-efficacy that is designed for the general population (12 years or older) and it has been tested in various countries.

**Secondary Outcome (Hopelessness):** We will assess hopelessness at baseline and at follow-up assessments using the Beck Hopelessness Scale (BHS). The BHS is a 20-item self-report scale that assesses hopelessness over the past seven days. Patients report on feelings about the future, loss of motivation, and future expectations. Total scores range from 0 to 20, with higher scores suggesting more hopelessness. The BHS has good reliability and validity and is sensitive to change. There is some evidence that the BHS may be a measure of risk of suicide.

**Secondary Outcome (Connectedness):** We will measure social connectedness using the Interpersonal Needs Questionnaire-15 (INQ-15). The INQ-15 is a 15-item self-report scale that measures thwarted belongingness and perceived burdensomeness. Each item is measured on a 7-point Likert scale, with higher scores suggesting lower perceived connectedness. The INQ-15 may be a measure of risk of suicide. In addition, we will add also administer the Multidimensional Scale of Perceived Social Support (MSPSS). The MSPSS is a 12-item self-reported scale that is designed to ask about support from several sources including friends, family and significant other. The scale has been shown to have good internal and test-retest reliability as well as good validity.

**Secondary Outcome (Suicide Attempts):** We will assess for non-fatal and fatal suicide attempts at one and three months after discharge using the C-SSRS. The C-SSRS is a valid and reliable scale that includes a seven-item subscale that asks patients to self-report on actual attempts, interrupted attempts, aborted attempts, and preparatory acts or

[figure not shown]

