### **Project Proposal, Phase 3, Aim 3**

To test our hypotheses as described above, we propose to conduct an assessor - blinded RCT comparing the BESST intervention plus standard care to standard care alone. We will enroll up to 25 patients who are 18 years or older and are being discharged from a VA-CCN mental health treatment setting. The primary aim is to determine whether the BESST intervention reduces suicidal ideation at one and three months after discharge. The secondary aim is to evaluate the impact of the BESST intervention on other related measures of suicide risk including hopelessness, social connectedness, fatal/non-fatal suicide attempts and treatment engagement.

**Randomization:** Prior to the start of study enrollment, the study team otherwise not involved in recruitment will independently prepare allocation cards using a permuted block schedule. The same study staff member will then put these prepared allocation cards into sealed, opaque, numbered envelopes. After obtaining consent and completing the baseline assessment (see description below), the study staff member will take the next numbered envelope from the box (described above) and open the envelope to determine the patient's assignment. In the event that the patient has been assigned to the intervention, the study staff will notify the intervention staff in order that the intervention staff can initiate the intervention. Otherwise, the patient will be informed that they have been assigned to usual care.

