## Research Protocol/Protocol Addendum Template

behaviors. The scale asks the assessor to document the actual and potential lethality of these behaviors. The C-SSRS is widely used in the VA.

**Secondary Outcome (Substance use):** We will assess substance use at baseline and follow-up assessments using a timeline follow-back approach. This method is commonly used in research studies to assess substance use patterns.

**Study Design:** As shown in **Figure 3** below, patients allocated to the BESST intervention will meet with the intervention staff around the time of discharge. During this visit, the patients will receive a brief educational intervention. Depending on patient preference, this visit will occur over the phone (or VA Video Connect). Depending on patient preference, the regular contacts will occur in a private office on the WRJ VAMC campus, or the contacts will occur over the phone (or VA Video Connect).

**Figure 3.** Schedule of Assessments and Interventions.

BIC= VA Brief Intervention and Contact Program; D/C = discharge; dy = days; m = months; MH = Mental Health; T0, T1, T2 = assessment time points; wk = weeks

All patients (including patients randomized to the intervention) will have access to standard care. Furthermore, regardless of study assignment, all patients will undergo outcome assessment at baseline (0M), one month (1M), and three months (3M). These assessments will be conducted by the independent outcome assessor. We anticipate that, in most cases, the baseline assessment will occur around the time of discharge. However, because patients will be recruited remotely, we anticipate that the baseline assessments may in some cases happen a few weeks after discharge. Depending on patient preference, the independent outcome assessor will conduct the follow-up assessments in a private office on the WRJ VAMC campus, over the phone, or using VA Video Connect. The assessors will be blinded to study assignment and the patients will be instructed to not reveal their status to the assessor.

Because we are recruiting patients from a large geographic area (New Hampshire, Maine and Vermont), we anticipate that several enrolled patients will prefer phone (or VA Video Connect) over in-person follow-up. Fortunately, the assessment instruments that we selected for this study can be administered over the phone or in person.

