### **Study Population and Recruitment**

We will coordinate with staff at the WRJ, Togus or Manchester VAMCs to gain lists of patients referred to or discharged from VA-CCN mental health treatment settings. Acquiring these lists is the most comprehensive and effective way to garner this group of patients. We may also coordinate with staff at the sites mentioned in staff meetings such as interdisciplinary rounds (IDR) to learn of eligible patients for our study. Once a patient has been identified, we will then go into the patient's medical record to confirm eligibility criteria are met and to obtain contact information including telephone numbers and street addresses. In addition, if feasible, the staff may also inform the patient about our study and ask the patient's permission for our study team to contact the patient to provide further information about the study. In this case, if permission is obtained, the staff member will document this information in the patient's medical record.

We will request a HIPAA waiver for screening purposes. For patients identified via medical records, study staff will mail them a brief letter explaining the study. We will then follow-up via phone approximately one week after mailing the letter. If patients are interested in the study, study staff will read a consent document to the patient, and the patient will decide whether they would like to participate. If they agree to participate, verbal consent will be obtained and recorded on the telephone consent document. For patients who are referred to us by treating mental health providers, we will call the patient to further discuss the study. The VA staff will document in the medical record that the patient has given permission for the study staff to contact the patient and to provide further information about the study. If the patients are interested in participating, study staff will complete the consent process via telephone or VVC.

In the case of the RCT, study staff involved in the recruitment and consent process will be blinded at the time of study allocation. During the course of the study, it will be impossible to blind the intervention staff or patients to treatment allocation; however, the outcome assessor will remain blind to study assignment throughout the trial. Patients will be instructed not to reveal their study assignment to the outcome assessor.

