### **Informed Consent**

We are requesting an alteration of consent. Because we are recruiting patients from VA-CCNs that are located across several states (many of which are located at a sufficient distance from the WRJ VAMC), it is not feasible for us to recruit patients in person to obtain their written consent. Furthermore, we wish to mitigate potential delays in recruiting patients because the goal of the intervention is to address the needs of patients around the time of discharge. Therefore, we will only be able to recruit patients virtually and conduct the consenting process virtually. Because this is a minimal risk intervention, it is appropriate to obtain a telephone consent or consent via VA-Video Connect (VVC) from the patient, with plans to send them a copy of the consent form by U.S. mail. This approach also reduces the burden on the patient, especially if they do not have access to technology and could otherwise not participate in the study because they can't sign a form electronically.

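### Time to first mental health appointment and three-month utilisation are counted from discharge, but allocation can come weeks later in some patients, so for a late entrant the first appointment may precede the arm assignment

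*Combined protocol and SAP*

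**What the plan says.** In the combined protocol and SAP, the paragraph Secondary Outcome (Patient Engagement) states "we will examine healthcare utilization in the first three months after discharge". It lists the amount of contact with mental health providers "as well as the time to first mental health appointment after discharge". Both clocks start at discharge.

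The Randomization paragraph (Project Proposal, Phase 3, Aim 3) places allocation later: "After obtaining consent and completing the baseline assessment (see description below), the study staff member will take the next numbered envelope". The Study Design paragraph expects that "in most cases, the baseline assessment will occur around the time of discharge", but because recruitment is remote it adds "we anticipate that the baseline assessments may in some cases happen a few weeks after discharge".

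The plan aims to be prompt. Baseline Assessment says "The study assessor will meet with each eligible patient as close to the time of discharge as possible", and Informed Consent says "we wish to mitigate potential delays in recruiting patients". Neither caps the delay, and the Inclusion Criteria require recent discharge without a number of days. For patients found through records, Study Population and Recruitment describes a mailed letter and then a call: "We will then follow-up via phone approximately one week after mailing the letter".

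Statistical Analyses, Specific Aim 2, gives a chi-squared test for the categorical utilisation measure and a mixed model for continuous outcomes. It names no time-to-event method and does not say how appointments before allocation are handled. A between-arm comparison of time to first appointment is implied, because the Project Proposal makes treatment engagement part of the trial's secondary aim.

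**The concern.** An outcome can show an effect of the arm only if it can still change once the arm is assigned. A patient who is first seen on day 10 and randomised on day 21 has a time to first appointment of 10 days in either arm. Such patients add no information on the intervention and pull the arms together.

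Utilisation has a milder form of the same problem: contacts made before allocation are counted in a window that is then compared by arm.

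Engagement is a secondary outcome. However, Specific Aims/Purpose names re-engagement in VA care as something the randomised trial is meant to determine, and with up to 25 patients there is little information to spare.

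**Working it through.** The plan gives no figure for either outcome, so there is none to reproduce. It also gives neither the share of late entrants nor their delay. The values marked *assumed* below are ranges, not estimates.

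**1. Share of the window before allocation.** Take three months as 91 days. For entry d days after discharge, the share is d/91. Delays of 1 to 4 weeks are *assumed*.

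- Week 1: 7/91 = 7.7%
- Week 2: 14/91 = 15.4%
- Week 3: 21/91 = 23.1%
- Week 4: 28/91 = 30.8%

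**2. Chance that the first appointment comes before allocation.** With a constant hazard and median m days (*assumed*), this is 1 − 0.5^(d/m).

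| Median m | Entry week 1 | Week 2 | Week 3 | Week 4 |
|---|---|---|---|---|
| 7 days | 50% | 75% | 88% | 94% |
| 14 days | 29% | 50% | 65% | 75% |
| 30 days | 15% | 28% | 38% | 48% |

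For the whole trial at m = 14:

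- If 25% enter at week 3, then 0.25 × 0.65 = 16%, or about 4 of 25 patients, have their outcome fixed in advance.
- If 10% enter at week 2, then 0.10 × 0.50 = 5%, or about 1 of 25.

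Early appointments are plausible for at least one group. Standard Care says that providers of patients on the High Risk for Suicide List must schedule four visits in the first 30 days. The number of such patients is not given.

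**3. Effect on the time-to-appointment comparison.** Simulation with 12 v 13 patients, hazard ratio 2.5 after allocation and 1 before it, median 14 days, and a two-sided log-rank test at 0.05 (all *assumed*; accurate to about two percentage points):

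| Late entrants | Power, clock from discharge | Power, clock from randomisation |
|---|---|---|
| 10% at week 2 | 53% | 58% |
| 25% at week 3 | 39% | 57% |

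The constant hazard also assumes that a patient already seen reaches the next appointment at the same rate as one not yet seen.

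**4. Effect on utilisation.** Assume a rate ratio of 1.5 after allocation and a constant visit rate. A patient entering at week 3 shows (21 + 1.5 × 70)/91 = 1.385. With 25% of such patients, the trial shows 0.25 × 1.385 + 0.75 × 1.5 = 1.47. The loss is small.

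**5. Would a 13-week utilisation count from randomisation do better?** Compare expected difference divided by its SD, with Poisson counts, 12 v 13 patients, 25% late by 21 days and rate ratio 1.5.

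*Constant rate, one visit per 14 days (6.5 in 91 days; assumed)*
- From randomisation: 3.25/√(9.75/12 + 6.5/13) = 2.84.
- From discharge: a late patient loses 0.5 × 6.5 × 21/91 = 0.75 visits of effect. The treated mean is 9.75 − 0.25 × 0.75 = 9.56, its variance is 9.56 + 0.1875 × 0.75² = 9.67, and the ratio is 3.06/√(9.67/12 + 6.5/13) = 2.68.

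*Front-loaded, four visits in 30 days and then one per 21 days (assumed)*
- From discharge: every control patient expects 4 + 61/21 = 6.90 visits. The treated mean is 0.75 × 10.36 + 0.25 × 8.96 = 10.01, with variance 10.01 + 0.1875 × 1.40² = 10.37. The ratio is 3.10/√(10.37/12 + 6.90/13) = 2.63.
- From randomisation: a late control patient expects 9 × 4/30 + 82/21 = 5.10. The control mean is 6.45 (variance 7.06) and the treated mean 9.68 (variance 11.05). The ratio is 3.23/√(11.05/12 + 7.06/13) = 2.67.

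So the gain nearly vanishes when visits are front-loaded. Counting from randomisation then also makes expected visits depend on delay even with no treatment effect. The SD of the between-arm difference from this source is (6.90 − 5.10) × √(0.25 × 0.75) × √(1/12 + 1/13) = 0.31 visits. From discharge it is zero.

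**The case against.** The strongest case is that discharge is the natural clinical origin. The stated problem is disengagement and suicide risk after discharge, and for someone already seen, a next appointment is a different thing from a first one. Most baselines are expected near discharge. The engagement paragraph also says that engagement is measured at baseline as well as at follow-up. Much of this stands. It is a reason to keep the discharge-based time as a descriptive measure, and it limits the size of the problem. It does not say how an appointment before allocation enters the arm comparison: Protected Health Information places abstraction of VA utilisation at the three-month follow-up.

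A reader might infer more than the documents support:

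- **Bias or false positives.** Events before allocation have the same distribution in both arms by randomisation, so the result is dilution, not systematic bias.
- **Chance imbalance in delay as an error in the utilisation outcome.** On the discharge clock every patient has the same window. Without a treatment effect, unequal delay creates no difference in expected contacts.
- **A need to re-anchor utilisation.** Step 5 shows little gain when visits are front-loaded. A shorter common window does worse than the plan: 9 weeks from randomisation gives 2.34 against 2.63 in the front-loaded case.

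The log-rank and rate-ratio figures describe analyses that the plan does not name. They show the order of size only. Figure 3 is not available here. It may settle when visits fall, but the text itself ties these two outcomes to discharge.

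**Conclusion.** The point holds, mainly for time to first mental health appointment. In a late entrant that outcome can be settled before allocation and then cannot reflect the arm. No text re-anchors the outcome or sets such appointments aside.

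The loss is small if few patients enter late (53% against 58% power with 10% at week 2). It is material if a quarter enter at week 3 (39% against 57%). Both figures rest on the assumed hazard ratio, median and constant hazard. For utilisation the dilution is modest (1.50 appears as 1.47 in the 25% case), and the discharge window can stay if contacts are split at randomisation.

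Severity is minor to moderate. Only a secondary outcome is affected, and the primary outcome is not touched by this point.

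**What to change.** 1. For the between-arm comparison, define time to first mental health appointment from randomisation and treat earlier appointments as baseline history. Keep the time from discharge as a descriptive measure.
2. Report days from discharge to randomisation by arm, so that readers can see how many patients entered late and by how much.
3. For utilisation, keep the planned abstraction but record contacts before and after randomisation separately, so that earlier contacts are not attributed to the arm. Give the days covered by the later part, which is shorter for late entrants (70 of 91 days at week 3).
4. Optionally, add a 13-week count from randomisation. If it is used, the analysis should take account of the discharge-to-randomisation interval. For late entrants this window also runs past the three months after discharge over which the Regular Contact paragraph describes the contacts, and abstraction may need to be later.

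The cost is wording plus one date that the trial already generates. Self-reported non-VA contacts would need approximate dates. The main downside is that, for a patient already seen, the randomisation-based outcome is a next appointment rather than the first after discharge; the retained descriptive measure covers this. No change to care is involved.
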